4.3 Exclusion criteria

The exclusion criteria for the initial Delta-TT study were:

- A. The subject is morbidly obese, defined as Body Mass Index (BMI) of > 40.
- B. The subject will be operated bilaterally.
- C. Patients having a deformity or disease located in other joints than the hip that needs surgery and is limiting their ability to walk.
- D. The subject has an active or suspected latent infection in or about the hip joint.
- E. Patient who is expected to need lower limb joint replacement for another joint within one year.
- F. The subject has a neuromuscular or neurosensory deficiency, which would limit the ability to assess the performance of the device.
- G. The subject has a systemic or metabolic disorder leading to progressive bone deterioration.

H. The subject's bone stock is compromised by disease or infection which cannot provide adequate support and/or fixation to the prosthesis.

I. Female patients planning a pregnancy during the course of the study.

For the 10-year follow-up study only the following exclusion criteria will be checked again:

J. The patient is unable or unwilling to sign the ICF specific to this study.

K. Subject deemed unsuitable for participation in the study based on the investigator's judgement.

4.4 Sample size calculation

RSA studies have a high degree of sensitivity and accuracy of measurements (Valstar et al., 2005). Therefore, relatively small patient groups are sufficient to detect between group differences. Sample size calculations in the initial study are based on a standard deviation of 0.3mm translation and 0.8° rotation for the uncemented cup (Baad-Hansen et al., 2011). At 10 years, we aim to include all 51 patients that were still included in the previous study at 5-years follow-up. Using Cohen's d, a difference of 1SD can be detected with 80% power and alfa 0.05, based on 16 patients in each group (<https://www.sealedenvelope.com/power/continuous-superiority/>).

5. TREATMENT OF SUBJECTS

< This chapter is only applicable for intervention studies >

Not applicable

6. INVESTIGATIONAL PRODUCT

6.1 Name and description of investigational product(s)

Delta-TT cup : a cementless press fit hemispheric cup with a TT structure made out of Titanium alloy. In the current study, this cup will be used with a standard highly cross linked polyethylene insert (UHMWPE X-Lima, LimaCorporate), as well as a ceramic insert (CeramTec GmbH, Plochingen, Germany).

https://limacorporate.com/repo/storage/834/file/B-5552-83-012-1_091900_FLY_DELTA-TT_EN_V2.pdf

H-MAX S femoral stem: a uncemented stem with Corail design philosophy in Titanium alloy with a Hydroxyapatite coated macro-textured surface. The stem is straight for a fast and effective osteointegration.

https://limacorporate.com/repo/storage/321/file/B-4250-83-000-1_111500_FLY_H-MAX-S_EN.pdf

A 32 mm ceramic head will be used (CeramTec GmbH, Plochingen, Germany).

https://www.ceramtec-medical.com/fileadmin/user_upload/Medical/Dokumente/Infocenter/Downloads-for-Health-Professionals/Product-Information/BILOXdelta-Quick-Reference-Guide.pdf

6.2 Summary of findings from non-clinical studies

The Delta-TT cup has been made with Trabecular Titanium (TT), which has osseointegration-promoting characteristics (Bondarenko et al., 2018; Massari et al., 2017). The porosity and pore size of the TT technology enhances vascularisation and mineralisation favouring new bone formation (Frosch et al., 2004; Karageorgiou & Kaplan, 2005). Besides, stem cells grown in TT scaffold have shown to adhere, proliferate and differentiate into osteoblastst (Benazzo et al., 2014; Gastaldi et al., 2010). The H MAX S stem has a hydroxyapatite coating for an effective osteointegration (Rokkum, Reigstad, & Johansson, 2002).

6.3 Summary of findings from clinical studies

Clinical studies have shown promising short- and mid-term outcomes of the Delta-TT cup in terms of bone incorporation without bone loss due to stress shielding (Massari et al., 2017). Besides, both the 2-year and 5-year results of our initial trial, showed stabilization of the Delta-TT cup and H MAX S stem (Klaassen et al., 2022).

6.4 Summary of known and potential risks and benefit

There is no guarantee that patients will personally benefit from inclusion in this study. Patients undergo a more thorough screening than non-study patients and may benefit from this added follow-up moment at 10-years postoperatively. Information gathered in this study may benefit others undergoing THA with uncemented components. Patients have already been randomized in the initial study and will only be evaluated by means of RSA imaging and questionnaires. There are, in our view, no risks associated with participation in this study. The effective radiation dose per RSA-radiograph is 70 μ Sv and is only administered at 1 follow-up moment. The additional annual radiation dose is negligible if the natural annual exposure of 2.5 mSv is considered and will do the patient no harm (Lewis, Blake, & Fogelman, 1994). The International Commission on Radiological Protection categorizes the corresponding level of risk qualitative due to radiation as “trivial” with a quantitative risk of about one in a million or less. The required level of benefit should be related to “only increase knowledge” (<http://ec.europa.eu/energy/nuclear>).

7. NON-INVESTIGATIONAL PRODUCT

<This chapter is applicable for any other product that is used in the study, like challenge agents or products used to assess end-points in the trial. This can be a medicinal product or a food product or a chemical compound or stable isotope or other product.

Not applicable

8. METHODS

8.1 Study parameters/endpoints

In general, data will be summarized by treatment group. For parameters represented by continuous variables, the summaries will consist of the mean and 95% confidence intervals. Continuous outcome variables will be analysed with parametrical statistical techniques, unless the normality assumption does not seem reasonable for the data, in which case non-parametric techniques will be considered.

For categorical variables, the number and percent in each category will be presented and will be analysed. Descriptive statistics for demographic, efficacy, and safety variables will be provided in tables. A two-sided 0.05 alpha level will be used.

8.1.1 Main study parameter/endpoint

The primary outcome in this study is long-term migration patterns of the Delta TT cup combined with the H-MAX S stem and compared between a ceramic and polyethylene liner, measured in 3D translations and rotations by means of RSA X-rays at 10-years postoperatively.

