8.1.3 Other study parameters

- Implant survival of the Delta TT cup and H-MAX S stem (Method: Revision yes / no; reason for revision; survival in years). Survival data will be collected from the Dutch Arthroplasty Register (LROI).
- Radiographic signs of osteolysis around the cup and the stem (Method: Radiolucent lines at X-ray, acetabular zones as described by DeLee and Charnley and Gruen zones around the stem. Orthopaedic surgeons will be blinded for liner type while evaluating the X-rays. Before the evaluation, the researcher will obscure the liner (and head) section on the X-rays.
- Clinical outcomes, obtained through Patient reported outcome measures (PROMs):
 - Pain at rest (NRS);
 - Pain during weight-bearing (NRS);
 - Quality of life (EuroQol 5-dimensions EQ5D-5L);

- Hip function by means of the Hip Disability and Osteoarthritis Outcome Score – Physical function Short form (HOOS-PS) and the Oxford Hip Score (OHS);
 - Self-reported squeaking
- Survival data at 10 years postoperatively will be related to the predicted survival at 2-years postoperatively, using the thresholds presented in the literature: Proximal cup translation on the Y-axis ≥ 1.0 mm at 2 years and for the stem subsidence ≥ 2.7 mm at 2-years postoperatively (Nieuwenhuijse et al., 2012; Pijls et al., 2012; Streit et al., 2016).

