10. STATISTICAL ANALYSIS

In general, data will be summarized by treatment group. For parameters represented by continuous variables, the summaries will consist of the mean and 95% confidence intervals. Continuous outcome variables will be analysed with parametrical statistical techniques, unless the normality assumption does not seem reasonable for the data, in which case non-parametric techniques will be considered.

For categorical variables, the number and percent in each category will be presented and will be analysed. Descriptive statistics for demographic, efficacy, and safety variables will be provided in tables. A two-sided 0.05 alpha level will be used.

Descriptive statistics and statistical comparisons for important demographic, efficacy, and safety variables will be provided in tables. A two-sided 0.05 alpha level will be used.

To assess cup and stem migration a mixed model analysis will be performed, with bearing (PE vs. CE) as the primary independent value of interest. Primary outcome will be the effect of bearing over the 10-year follow-up period on implant migration. Group differences will be separately analysed at each time point including time as a categorical factor variable and a time-by-group interaction term. Differences are considered significant for p-values below 0.05.

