10.1 Primary study parameter(s)

The main study parameter is migration of the Delta TT cup compared between a polyethylene and ceramic insert by means of RSA imaging at 10 years postoperative. RSA data will be analyzed using mixed model analysis with bearing (CE vs PE) as a primary independent value of interest.

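### The primary cup endpoint has several migration components and no lead one, each judged at p<0.05, while the sample size covers a single comparison

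*Protocol*

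**What the plan says.** - Section 8.1.1 makes cup migration the primary outcome, compared between ceramic and polyethylene liners and "measured in 3D translations and rotations by means of RSA X-rays at 10-years postoperatively". No axis, summary measure or order of testing is given there, in the Summary, or in sections 2, 10 or 10.1.
- Section 10 defines the primary effect in the mixed model: "Primary outcome will be the effect of bearing over the 10-year follow-up period on implant migration". It then adds: "Group differences will be separately analysed at each time point including time as a categorical factor variable and a time-by-group interaction term".
- The decision rule in section 10 is general: "Differences are considered significant for p-values below 0.05", with a two-sided alpha of 0.05.
- Section 10.1 places the main parameter at a single time, 10 years after surgery, and again speaks only of cup migration.
- Section 4.4 quotes one SD for translation (0.3 mm) and one for rotation (0.8°). It then gives 16 patients per group as enough to detect a 1 SD difference with 80% power at alpha 0.05.
- Section 8.1.3 singles out one cup axis, "Proximal cup translation on the Y-axis", but only as the 2-year threshold for predicting survival.

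**The concern.** The protocol spends one test's worth of alpha on a primary outcome with several variables. A reader of the final report could not tell which p-value answers the primary objective. A chance result on one axis could be presented as a liner effect, and null results on the other axes could be stressed or passed over. The two descriptions of the primary effect add to this, because an effect over the whole follow-up and a contrast at 10 years are different quantities and can give different p-values for the same component. What is at stake is the error rate of the trial's main conclusion about liner type.

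**Working it through.** **Inputs.** Components: 3 translations + 3 rotations = 6 (implied by section 8.1.1, not stated as a count). Threshold: two-sided 0.05 per difference (section 10). Design: 1 SD, 80% power, 16 per group (section 4.4). Patients: 25 and 27 randomised, at most 51 available at 10 years (sections 3 and 4.4). Correlation between components: not given, so a range is assumed.

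**1. The plan's own figure.** For one comparison, n per group = 2 × (1.960 + 0.842)² = 15.7, rounded up to 16. Normal-approximation power at 16 per group is 80.7%. The figure is reproduced, and it is for a single test. (The t-based version needs 16.7, so 17 per group, a trivial difference.)

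**2. Six components at 10 years, independent.** The chance of at least one p<0.05 when there is no liner effect is 1 − 0.95⁶ = 1 − 0.735 = 0.265.

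**3. Six components at 10 years, correlated.** Six equally correlated standard normal test statistics were simulated (400,000 draws), and the share with any |Z| above 1.96 was counted:

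| Assumed correlation | Chance of at least one false positive |
|---|---|
| 0 | 26.5% |
| 0.3 | 24.1% |
| 0.5 | 20.7% |
| 0.7 | 16.5% |
| 0.8 | 13.7% |
| 0.9 | 10.9% |
| 1 | 5.0% |

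For jointly normal statistics and two-sided tests, independence gives the highest rate (Šidák's inequality). So 26.5% is a ceiling for this family of six, not a floor.

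**4. What adjustment would cost.** Bonferroni over six uses 0.05/6 = 0.0083. Then n per group = 2 × (2.638 + 0.842)² = 24.2, so 25 (27 on the t-based calculation). Power for 1 SD, t-based:
- 16 per group: 51%.
- All 51 patients, assumed split 25/26: 79%.

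Holm is never less powerful than Bonferroni, so these are lower bounds for it. The 51-patient figure is a best case, because section 4.2 excludes revised hips from RSA imaging. Both figures treat the mixed-model contrast as a two-sample comparison, as section 4.4 does.

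**The case against.** The strongest reply has four parts.

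- *The SAP may settle it.* The SAP is not shown, and multiplicity procedures are often placed there. That is fair for the method of adjustment. It does not cover a protocol that itself fixes a multi-component primary outcome, a flat p<0.05 rule and a one-test sample size. A SAP that later named one axis would be narrowing the protocol after results to 5 years were known.
- *The protocol never says that one significant component is enough.* This is true, and the error rates above depend on that reading. But no other rule is stated, and section 10 calls each such difference significant.
- *A spurious liner difference would go against the stated hypothesis of good stability with either liner.* Also true, and it lowers the urgency. The primary objective is still a comparison of liners, and a false difference would be a wrong answer to it.
- *Adjustment is affordable.* With all 51 patients it is, at about 79% power. The loss to 51% arises only at 16 per group, so the power argument does not rule out adjusting.

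Two stronger readings are tempting and should be resisted. A reader might infer that the error rate is at least 21%; that holds only for correlations up to about 0.5, and the protocol gives none. A reader might also count six components at all seven post-baseline visits as 42 primary tests. Section 10 does not call the by-visit contrasts primary, and the Summary already reports the 2- and 5-year liner differences as small and not significant. Those visits are therefore not open chances for a false positive.

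**Conclusion.** The point holds in limited form. The protocol names a primary outcome with six implied components and no lead, applies p<0.05 to each difference, and sizes the study for one test. If any significant component is taken as a liner effect, the false-positive rate at 10 years alone lies above 5% and up to about 26%, depending on correlations that the documents do not give. It would be higher if by-visit contrasts were also taken as primary, but the documents do not establish that they are. Separately, section 10 disagrees with sections 8.1.1 and 10.1 on whether the primary effect is over the whole period or at 10 years. Severity: should be fixed before the 10-year data are analysed.

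**What to change.** State in sections 8.1.1, 10 and 10.1 one primary cup component, one effect and one time point. Proximal (Y-axis) translation at 10 years, tested at two-sided 0.05, is one candidate, since section 8.1.3 already takes that axis from the literature. Report the other five components and the earlier visits as secondary, with 95% confidence intervals and no claim of significance. The 16 per group in section 4.4 then stands.

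Alternatively, keep all six components as primary at 10 years with a Holm adjustment, and restate the power in section 4.4 for the number of patients expected to contribute RSA data.

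Either route costs wording only and needs no new data. With a single component, an isolated effect on another axis becomes a secondary finding. Because results to 5 years are known, the choice of axis must be justified on external grounds and recorded before the 10-year analysis.

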8.1.2 Secondary study parameters/endpoints

Secondary endpoints at 10-years postoperatively are:

- Long-term migration patterns of the H-MAX S stem, expressed in 3D translations and rotations (Method: RSA X-rays).

8.1.3 Other study parameters

- Implant survival of the Delta TT cup and H-MAX S stem (Method: Revision yes / no; reason for revision; survival in years). Survival data will be collected from the Dutch Arthroplasty Register (LROI).
- Radiographic signs of osteolysis around the cup and the stem (Method: Radiolucent lines at X-ray, acetabular zones as described by DeLee and Charnley and Gruen zones around the stem. Orthopaedic surgeons will be blinded for liner type while evaluating the X-rays. Before the evaluation, the researcher will obscure the liner (and head) section on the X-rays.
- Clinical outcomes, obtained through Patient reported outcome measures (PROMs):
 - Pain at rest (NRS);
 - Pain during weight-bearing (NRS);
 - Quality of life (EuroQol 5-dimensions EQ5D-5L);

- Hip function by means of the Hip Disability and Osteoarthritis Outcome Score – Physical function Short form (HOOS-PS) and the Oxford Hip Score (OHS);
 - Self-reported squeaking
- Survival data at 10 years postoperatively will be related to the predicted survival at 2-years postoperatively, using the thresholds presented in the literature: Proximal cup translation on the Y-axis ≥ 1.0 mm at 2 years and for the stem subsidence ≥ 2.7 mm at 2-years postoperatively (Nieuwenhuijse et al., 2012; Pijls et al., 2012; Streit et al., 2016).

8.2 Randomisation, blinding and treatment allocation

Not applicable

8.3 Study procedures

RSA procedure:

The RSA set-up consist of two synchronized roentgen tubes positioned approximately 1.5 meter above two roentgen cassettes (35 X 43 cm) at a 20° angle to the vertical. Both roentgen tubes simultaneously expose the roentgen film (Figure 2). A calibration box is used to calibrate the experimental set-up.

The baseline RSA X-ray which was taken within three days after surgery and before weight bearing is used as baseline. Since the tantalum balls are fixed in the bone around the implants, the position of the implant relative to the bone can be calculated. Taking these bone markers as reference points, the spatial translations and rotations of the component during follow-up can be calculated (Kaptein, Valstar, Spoor, Stoel, & Rozing, 2006; Valstar et al., 2005). The bone markers need to be well fixated in the bone. Bone markers are defined unstable when they move more than 0.3 mm with respect to the other bone markers. Unstable markers will be excluded from analysis (Garling, Valstar, & Nelissen, 2005).

[figure not shown]

Figure 1: A uniplanar RSA arrangement. Two X-ray tubes are focused on the joint under examination. A calibration cage is placed underneath the X-ray table. It holds two X-ray films positioned next to each other.

The 10-year RSA X-rays will ideally be completed within 20 weeks after reaching date of 10-years postoperatively. An independent party, *RSACore* of the Department of Orhopaedics of LUMC will be responsible for the analysis of the RSA images. The anonymous RSA images can be directly uploaded to the secure website of the *RSACore*. *RSACore* will perform the RSA related data analysis and provide a report after completion of the study.

8.4 Withdrawal of individual subjects

Subjects can leave the study at any time for any reason if they wish to do so without any consequences. The investigator can decide to withdraw a subject from the study for urgent medical reasons.

8.5 Replacement of individual subjects after withdrawal

Since this is a long term follow-up study, patients who withdraw from the study cannot be replaced.

8.6 Follow-up of subjects withdrawn from treatment

Not applicable; this study does not include treatment.

8.7 Premature termination of the study

The investigator will notify the accredited Medical research Ethical Committee (METC) of the end of the study within a period of 8 weeks. The end of the study is defined as the last patient's visit which is estimated March 2026. The sponsor will notify the METC immediately of a temporary halt of the study, including the reason of such an action. In case the study is ended prematurely, the sponsor will notify the accredited METC within 15 days, including the reasons for the premature termination. Within one year after the end of the study, the

investigator/sponsor will submit a final study report with the results of the study, including any publications/abstracts of the study, to the accredited METC.

9. SAFETY REPORTING

9.1 Temporary halt for reasons of subject safety

In accordance to section 10, subsection 4, of the WMO (in Dutch: Wet Medisch-wetenschappelijk Onderzoek), the sponsor will suspend the study if there is sufficient ground that continuation of the study will jeopardise subject health or safety. The sponsor will notify the accredited METC without undue delay of a temporary halt including the reason for such an action. The study will be suspended pending a further positive decision by the accredited METC. The investigator will take care that all subjects are kept informed.

9.2 AEs, SAEs and SUSARs

All participants in this study had THA 10 years ago and received a Delta TT cup with ceramic head and either a ceramic- or a polyethylene liner and a H-MAX S stem. They were followed for adverse events up until 5-year follow-up or until lost to follow-up. Adverse events as defined in the protocol of the initial study and were reported in toetsingonline. This 10-year follow up study has a cross-sectional design and includes only one single follow-up moment and visit to the hospital. Prior to this visit, patients will be queried about any medical procedures performed on either the affected and unaffected hip joint. These data will be utilized for data analyses, but will not be reported as a serious adverse event (SAE) because these events did not occur during the study. Following the visit, participants will not be followed up.

10. STATISTICAL ANALYSIS

In general, data will be summarized by treatment group. For parameters represented by continuous variables, the summaries will consist of the mean and 95% confidence intervals. Continuous outcome variables will be analysed with parametrical statistical techniques, unless the normality assumption does not seem reasonable for the data, in which case non-parametric techniques will be considered.

For categorical variables, the number and percent in each category will be presented and will be analysed. Descriptive statistics for demographic, efficacy, and safety variables will be provided in tables. A two-sided 0.05 alpha level will be used.

Descriptive statistics and statistical comparisons for important demographic, efficacy, and safety variables will be provided in tables. A two-sided 0.05 alpha level will be used.

To assess cup and stem migration a mixed model analysis will be performed, with bearing (PE vs. CE) as the primary independent value of interest. Primary outcome will be the effect of bearing over the 10-year follow-up period on implant migration. Group differences will be separately analysed at each time point including time as a categorical factor variable and a time-by-group interaction term. Differences are considered significant for p-values below 0.05.

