1. INTRODUCTION AND RATIONALE

Aseptic loosening of the acetabular component of hip implants in total hip arthroplasty (THA) remains one of the main causes of long-term implant failure and revision (LROI, 2023; NJR, 2023; NJRR, 2023). Aseptic loosening is often induced by wear of polyethylene liners, causing osteolysis around the implant. Highly cross-linked polyethylene liners have been developed to reduce the risk of wear. Ceramic has a higher stiffness and ceramic-on-ceramic (CoC) shows even lower wear rates compared to ceramic on polyethylene. However, the inelasticity of a CoC bearing might hamper a natural load transfer to the bone, potentially causing increased micromotion and thereby affect implant stability in press-fit THA (Small et al., 2013; van Loon et al., 2023).

The Delta-TT cup and H MAX S stem have been developed, aiming to optimize initial stability and osseointegration of the implant (LimaCorporate, Villanova San Daniele del Friuli, Italy). Radiostereometric Analysis (RSA) is a very accurate measurement technique to determine micromotion of the implant relative to inserted tantalum markers in the surrounding bone and has been the recommended means in evidence-based phased introduction of new implants (Swierstra et al., 2011). It is believed that early RSA migration patterns at 2 years postoperatively can predict implants at risk for long-term aseptic loosening (Nieuwenhuijse, Valstar, Kaptein, & Nelissen, 2012; Pijls et al., 2012; Streit et al., 2016)

In our initial Delta-TT study, we used RSA imaging to compare early migration patterns of the Delta-TT cup and H MAX S stem between polyethylene and ceramic liners. A trend towards increased migration was observed in Delta TT cups combined with ceramic liners, however between-group effects were small and not statistically significant. The 2-year results showed stabilization of Delta-TT cups within 6 months, regardless of liner type (Klaassen et al., 2022). Similarly, the 5-year results showed comparable migration patterns of the Delta TT cup and H MAX S stem between ceramic and polyethylene liners. These results indicate that after initial migration, implants in both groups showed secondary stabilization, which is promising for long-term survival of the implant.

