2. OBJECTIVES

Primary Objective:

- To compare long-term stability of the Delta TT cup between ceramic and polyethylene liners, by means of RSA at 10-years postoperatively.

Secondary Objectives:

- To compare long-term stability of the H MAX S stem between ceramic and polyethylene liners, by means of RSA at 10-year postoperatively.
- To measure implant survival rates, reasons for revision and radiographic signs of osteolysis and compare these outcomes between ceramic and polyethylene liners.
- To compare clinical outcomes and patient-reported outcome measures (PROMs) for the Delta TT cup with H MAX S stem, between the ceramic and polyethylene group.
- To compare the survival data at 10-years postoperatively with the predicted survival at 2-years postoperatively using the thresholds presented in the literature. The aim is to measure the predictive value and quantify how well RSA analysis at 2-years predicted survival for the uncemented press-fit components used in this study.

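### Section 10 makes the liner effect over the whole follow-up the primary outcome, while the objective, main endpoint, section 10.1 and sample size point to the difference at 10 years

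*Protocol*

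**What the plan says.** Section 10 defines the primary analysis of the mixed model: "Primary outcome will be the effect of bearing over the 10-year follow-up period on implant migration". The sentence after it adds: "Group differences will be separately analysed at each time point including time as a categorical factor variable and a time-by-group interaction term".

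Elsewhere the primary question sits at one time point:

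- Section 2, primary objective: "To compare long-term stability of the Delta TT cup between ceramic and polyethylene liners, by means of RSA at 10-years postoperatively".
- Section 8.1.1, main endpoint: "measured in 3D translations and rotations by means of RSA X-rays at 10-years postoperatively".
- Section 10.1: cup migration "compared between a polyethylene and ceramic insert by means of RSA imaging at 10 years postoperative". It then repeats that a mixed model with bearing as the main independent variable will be used, without naming a contrast.
- Section 4.4: a difference of 1 SD, 80% power, alpha 0.05 and 16 patients per group.

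Section 3 lists six post-baseline RSA visits in the initial study: 6 weeks, 3 months, 6 months, 1 year, 2 years and 5 years. The present study adds one, at 10 years (sections 3 and 9.2). On the earlier data, section 1 reports: "The 2-year results showed stabilization of Delta-TT cups within 6 months, regardless of liner type". The Summary and section 1 add that between-group effects were small and not statistically significant, with a trend towards more migration with ceramic liners.

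**The concern.** An effect of bearing over the period and a difference at 10 years are different contrasts. They agree only when the liner difference is the same at every visit. Six of the seven post-baseline visits come from the initial study, and four of the seven fall in the first year. An effect pooled over visits therefore rests mainly on data in hand before this follow-up began.

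Two errors become possible. A liner difference that emerges late could leave the primary test negative. An early difference that later disappears could make it positive with nothing left at 10 years. Because the protocol supports both definitions, the primary conclusion can depend on which one the analyst follows.

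**Working it through.** **The plan's own figure.** Section 4.4, two means, difference 1 SD, two-sided alpha 0.05, 80% power:

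n = 2 × (1.960 + 0.842)² / 1² = 15.7, so 16 per group. Power at 16 is Φ(√(16/2) − 1.960) = Φ(0.868) = 80.7%. The t-based value is 78.1%. The figure reproduces, and it is a two-sample comparison at one time point. It therefore matches the 10-year contrast and not a pooled effect.

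**Inputs.** Seven post-baseline visits (section 3). SD 0.3 mm and 0.8° (section 4.4). 51 patients, taken as 25 v 26; 24 v 27 gives the same result to the nearest percent.

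**Assumptions, because the protocol gives no covariance.** Equal SD at each visit. Correlation ρ from 0.3 to 0.9, either compound symmetry or AR(1) in visit order. The whole-period effect is read as a weighted average over the seven visits.

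**Weight of the 10-year visit.**

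- Equal weights, which are also the GLS weights under compound symmetry: 1/7 = 14%.
- AR(1) with GLS weights: 1/(7 − 5ρ) = 1/5.5 = 18% at ρ = 0.3, and 1/2.5 = 40% at ρ = 0.9.

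**A 1 SD difference at 10 years only.** The equal-weight average is 1/7 = 0.14 SD, that is 0.3/7 = 0.043 mm or 0.8/7 = 0.11°.

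- Compound symmetry: the variance of the mean is (1 + 6ρ)/7. The standardised effect is (1/7)/√((1 + 6ρ)/7) = 0.23 at ρ = 0.3 and 0.15 at ρ = 0.9.
- AR(1), GLS: the variance is (1 + ρ)/(7 − 5ρ). The standardised effect is 0.182/√0.236 = 0.37 at ρ = 0.3 and 0.400/√0.760 = 0.46 at ρ = 0.9.

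**Power from the noncentral t distribution, 25 v 26, ρ from 0.3 to 0.9:**

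| True liner difference | Pooled, compound symmetry | Pooled, AR(1) with GLS | 10-year contrast |
|---|---|---|---|
| 1 SD at 10 years only | 8–12% | 26–36% | 94% |
| 0.5 SD at 5 years, 1 SD at 10 | 12–22% | 38–42% | 94% |
| Linear growth to 1 SD at 10 years | 17–32% | 42–57% | 94% |
| 1 SD at the six earlier visits, none at 10 | 88–99.7% | 67% to over 99.9% | 5% (alpha) |
| Constant 1 SD | at least 95% | at least 98% | 94% |

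At 16 per group, the first row becomes 7–10% (compound symmetry) and 18–24% (AR(1)), against 78–81% for the 10-year contrast.

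**The case against.** The strongest reply is that the 10-year contrast is already planned. The sentence following the definition asks for group differences at each visit through a time-by-group interaction. This stands. A reader might infer that a late liner effect would go undetected, but the protocol does not support that: the effect would be estimated and tested, only not as the primary result.

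Second, the protocol specifies no seven-visit average. Migration is measured from the postoperative baseline (section 8.3), so migration at 10 years is itself movement accumulated over the period, and the sentence in section 10 can be read that way. The Summary and section 8.1.1 also speak of migration patterns, which suits a longitudinal effect. This stands as well. With an interaction in the model, an effect of bearing could mean an average over visits or the difference at a reference visit. The defect is an unresolved conflict, not a settled choice of a poor contrast.

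Third, the 8–12% figure is near the worst case. It needs no difference at six visits followed by a full 1 SD at the seventh. The reported early trend makes that pattern less natural, and the other rows of the table are milder. The 94% is optimistic in turn: it needs evaluable RSA from all 51 patients, while section 4.2 expects some revised patients, who will have no RSA.

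Two further inferences go beyond the text. One is that each of the six earlier visits was reported as not significantly different; the protocol summarises the 2- and 5-year results as a whole. The other is that selective reporting is intended; nothing suggests it. A statistical analysis plan that is not at hand may name the contrast, but the protocol's statements would still disagree with each other.

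**Conclusion.** The inconsistency is real and nothing in the protocol resolves it. One sentence in section 10 points to the whole period. The objective, the main endpoint, section 10.1 and the sample size point to 10 years. The choice can change the primary conclusion in either direction when the liner difference varies over time, and it costs nothing when the difference is constant.

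The finding that the passages conflict rests on the text alone. The power figures also depend on reading the whole-period effect as an average over visits, on equal SD per visit and on the assumed correlations. They show how far the two readings can diverge; they are not the power of this trial.

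**What to change.** In section 10, replace the sentence that defines the primary outcome with: *The primary estimate is the ceramic minus polyethylene difference in cup migration at 10 years, from the time-by-group term of the mixed model, with 95% CI.* State that the effect over the whole follow-up is secondary, and name the same contrast in section 10.1. This settles the time point; it does not by itself say which translation or rotation the estimate refers to.

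Optionally, add as supportive the change to 10 years from one earlier visit named in advance. Leaving that visit open would create a new choice.

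The cost is wording in two sections, with the same model and data. The only loss is the primary status of the whole-period effect. The change should be made before the 10-year data are analysed.
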